#### 9.4 Study Design:

Describe study design in one to two sentences (e.g., prospective, use of existing records/data /specimens, observational, cross-sectional, interventional, randomized, placebo-controlled, cohort, etc.). Specify the phase – Phase I, II, III, or IV – for FDA-regulated investigational drug research

This study utilizes a single-blinded, randomized controlled non-inferiority trial design.

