Study participants whose randomized dosing regimens are rejected by the attending provider will be excluded from the study. Again, attending provider concurrence with the randomized ketorolac dosing utilized in this study will be documented on the Ketorolac Research Form and is reviewed in the inclusion and exclusion portion of this application.

Prior to administration of ketorolac, a review of systems (ROS) will be performed with each patient to ensure that the subject has no medical history or other acute medical problems which would meet exclusion criteria for this study. However, this information will not be documented on any forms and will not be accessed through the EHR. The ROS is an anatomic or physiologic systems based detailed

interview with the patient to discuss their overall health and to identify any other medical issues that may or may not be connected with the patient's reason for ED visit.

The ROS used for this study is located within this application and will be located in the appendix of the manuscript when this study is complete. The study investigators' ROS may be separate from the actual attending provider ROS. The attending provider will perform their own ROS based on standard medical history taking. However, the ROS performed by the investigators for the purpose of this study will be used to discover any other medical issue or issues which may meet inclusion or exclusion criteria. If deemed pertinent to patient care, information obtained by performing the investigator ROS will be communicated verbally to the attending provider, so that they are aware that the patient may require evaluation for medical issues beyond an acute MSK injury or pain.

Ketorolac will be prepared for IM injection by the nursing staff assigned to the patient once the following have taken place:

1. Study subject has granted consent
2. Pregnancy is excluded
3. Breast feeding is excluded
4. Inclusion criteria are met
5. None of the exclusion criteria are met
6. The ROS is complete
7. The attending provider agrees to the randomized dose and formally prescribes the randomized dose of ketorolac through the EHR
8. Ketorolac will then be prepared for IM injection by the nursing staff assigned to the patient

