All appropriate provider and nursing policies, safeguards and regulations governing the preparation and administration of parenteral medication within the WBAMC ED will be followed and standard of care for the injection of ketorolac will not be altered, omitted or deviated from industry, ethical, moral or hospital standards. The investigators will not have any part in preparation or administration of the ketorolac-this will be completely handled by WBAMC ED nursing staff and the order for the ketorolac will have already been approved and prescribed by the WBAMC attending ED provider through the EHR.

As the medication is prepared for administration, the investigator will educate the subject on the use of the VAS and annotate their pre-treatment pain score on the VAS form. For the purposes of this study, the VAS is a validated tool that will be used to objectively measure the subject's response to ketorolac.

The subject will then be injected intramuscularly with the dose of ketorolac randomized to the patient based on the Subject Study Number assigned to the randomized packet, which was assigned to that subject. Again, all appropriate provider and nursing policies, safeguards and regulations governing the preparation and administration of parenteral medication within the WBAMC ED will be followed and standard of care for the injection of ketorolac will not be altered, omitted or deviated from industry, ethical, moral or hospital standards.

Following the administration of ketorolac and at the 30 and 60 minute intervals, VAS scores will be recorded, the patient will be assessed for adverse effects (objective and subjective) and blood pressure and heart rate measurements will be taken. At the conclusion of the 60 minute period and documentation of the VAS and any adverse effects, the data collection phase will be considered complete. The subject will be notified that the study has concluded. The attending provider will then continue with evaluation, treatment, and disposition, as indicated.

As outlined during the consent process, additional analgesia will be available during the course of the study. The decision to provide additional analgesia will be made by the attending provider in consideration of the study subject's clinical scenario. Study subjects who receive additional analgesia will be unenrolled from the study at the time of administration of the additional analgesia.

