**10.14 Managing Data (Data Management and/or Sharing Plan) and/or Human Biological Specimens for this Study:**

Include in this section the plan for acquiring data (both electronic and hard copy), access during the study, data/specimen storage and length of time stored, shipment/transmission, and the plan for storage and final disposition at the conclusion of the study. Describe any data agreements in place for accessing data within and/or outside of your institution (e.g., Data Sharing Agreement, Data Use Agreement, Business Agreements, etc.)

As outlined in the procedures section, data acquired will initially be obtained by the investigator via T-system™ home screen during the pre-screening process. Data collection will occur from the time the subject provides informed consent through the conclusion of the data collection period. As the primary outcome, subjective pain level will be obtained upon administration of intramuscular ketorolac then 30 and 60 minutes after administration. As the secondary outcome, adverse effects will be assessed for at 30 and 60 minutes after administration of intramuscular ketorolac. Descriptive statistics will also be obtained on the Ketorolac Research Form after informed consent is obtained.

The subjective pain levels will be annotated on the three VAS forms. The descriptive data and adverse effects will be annotated on the WBAMC Ketorolac Research Form. These forms will be placed within the document envelopes for the duration of the study. At the end of each study day, the data from each

study subject will be transcribed on to the Excel document on the PIs government issued laptop. The laptop will physically be in the PIs possession for the duration of the study.

The only human biological specimen which will be obtained will be urine. It will be used for a POC UHCG test in order to assess for pregnancy. These specimens will be obtained, handled, processed, and destroyed in accordance with WBAMC ED and hospital policies. The results of the POC UHCG will be reported verbally to the attending and/or via the T-System comments section in EHR, which does not require access to the subject's individual EHR for their specific ED encounter.

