### **11.0 Statistical/Data Analysis Plan**

#### **11.1 Statistical Considerations:**

List the statistical methods to be used to address the primary and secondary objectives, specific aims, and/or research hypotheses. Explain how missing data and outliers will be handled in the analysis. The analysis plan should be consistent with the study objectives. Include any sub-group analyses (e.g., gender or age group). Specify statistical methods and variables for each analysis. Describe how confounding variables will be controlled in the data analysis

The primary outcome will be the difference in VAS from baseline to 30 minutes and from baseline to 60 minutes. Our research hypothesis is that the measured pain relief using 15mg of intramuscular ketorolac will be non-inferior to the measured pain relief using 60mg of intramuscular ketorolac. Whereas in a clinical study where the research hypothesis is that one treatment, say drug A, is demonstrated to have a better (improved pain relief) outcome than the second treatment, say drug B, we are hypothesizing that smaller dose drug is not inferior in terms of pain relief than the higher drug dose. We fully suspect that the higher drug dose will have a better average outcome, but the question of interest is, is the outcome for the lower dose drug non-inferior to that of the higher drug dose. The analysis used in this study is a non-inferiority test. This hypothesis can be tested using a variety of methods that involve the construction of one-sided confidence interval or one-sided, two-sample equal-variance t-test with alpha of 0.05. In both methods, the power and sample size can be computed.

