**11.5 Please provide a justification for your sample size**

In this study, we assume that we are comparing the mean VAS between the 2 Groups, and the margin of non-inferiority is -13 mm. The actual difference between the means is assumed to be 0 and the standard deviation is assumed to be 27 for the 2 Groups (estimated from the Motov manuscript). Group sample sizes of 55 and 55 achieve 80% power to detect non-inferiority using a one-sided, two-sample equal-variance t-test with alpha of 0.05. The sample size per arm was increased from 55 to 61 to account for an anticipated 10% dropout or withdrawal of subjects (5.5 subjects was rounded to 6 subjects).

**11.6 Data Analysis Plan: Complete description: Background, Objectives, Design, Step by Step how the project is going to be done, Data analysis plan:**

To test for non-inferiority of dose 15mg to dose 60 mg using the VAS pain score, the analysis to be used is called an interval test. The hypothesis will be tested using the construction of one-sided confidence intervals or one-sided, two-sample equal-variance t-test with alpha of 0.05. To test that the lower dose has less adverse effects, we will use the one-sided z-test for testing two independent proportions. All tests will be conducted at the 0.05 level of significance.

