Cover Page

Title: Comparison of Intramuscular Ketorolac at Two Single-Dose Regimens for Treatment of Acute Musculoskeletal Pain in a Military Emergency Department: A Randomized Controlled Non-Inferiority Trial

NCT: Not received yet

Date: 2/5/2021

Statistical Analysis Plan

Data analysis will be performed using the statistical software SPSS (IBM SPSS Statistics for Windows, Version 26.0. Armonk, NY: IBM Corp.). The primary outcome will be tested using an independent samples *t*-test. To assess for any differences in VAS scores based on demographic data, independent *t*-tests will be utilized. To assess for normality of distributions in the sample's continuous demographic and clinical characteristics, z-scores will be formed by dividing skewness by the standard error of skewness. This is performed to ensure that parametric measures can be used for the two groups. A Fisher's exact test will be used to assess the lower dose for a difference in adverse effects. During analysis, it was determined that the pain reduction variables could be compared by age and body weight using Pearson correlations. Additionally, the pain reduction variables will be compared by gender, duration of pain (\leq 24 hours vs. $>$ 24 hours), and location of pain (back/neck vs. other locations and small vs. large joints) using independent *t*-tests.

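### The only baseline VAS the protocol describes is obtained once the investigator knows the dose, so one of the two terms of the primary change score is open to influence by arm

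*Protocol*

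**What the plan says.** Protocol section 11.1 defines the endpoint: "The primary outcome will be the difference in VAS from baseline to 30 minutes and from baseline to 60 minutes". For the analysis, the SAP says "The primary outcome will be tested using an independent samples" *t*-test. Protocol section 11.6 likewise gives a one-sided interval or two-sample t-test. Neither document specifies adjustment for baseline in the primary comparison.

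The order of events is in Protocol section 10.1:

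- **Packets.** Under Randomization and Study Subject Packet Creation, packets are made up before screening. The Subject Study Number contains 15 or 60, which is the dose. It is written on the packet and on every form inside, including the consent form and the VAS forms.
- **Attending provider.** Under Medication Administration, the investigator tells the attending provider the randomised dose. The seventh step in the list before injection reads "The attending provider agrees to the randomized dose and formally prescribes the randomized dose of ketorolac through the EHR". Drug preparation is the eighth.
- **Baseline.** Only then: "As the medication is prepared for administration, the investigator will educate the subject on the use of the VAS and annotate their pre-treatment pain score".

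Section 10.14 describes the timing differently: "subjective pain level will be obtained upon administration of intramuscular ketorolac then 30 and 60 minutes after administration". Section 9.4 says "This study utilizes a single-blinded, randomized controlled non-inferiority trial design" and does not state who is blinded.

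**The concern.** A baseline is normally protected by being recorded before anyone involved knows the allocation. Here the person who teaches the scale and obtains the mark already knows the arm, and the trial's hypothesis is that the lower dose is not inferior. The endpoint is a raw change, so a difference between arms in how the baseline is elicited passes into the treatment estimate unless the same influence also acts on the follow-up marks. If the 15 mg baseline sits a little too high, pain reduction on 15 mg looks larger and the result moves toward non-inferiority. If it sits too low, a true non-inferiority result may be missed. Baseline comparability of the arms also stops being a clean check on randomisation. This applies to every subject, whatever the severity of pain at entry.

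**Working it through.** **Inputs (Protocol section 11.5).** "the margin of non-inferiority is -13 mm"; "the standard deviation is assumed to be 27 for the 2 Groups"; assumed true difference 0; 55 evaluable per arm; one-sided alpha 0.05; 80% power.

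**1. The plan's own figure.** Normal approximation: n = 2 × (1.645 + 0.842)² × 27² / 13² = 53.3, so 54 per arm. The noncentral t gives power 0.7998 with 54 per arm and 0.806 with 55. The stated 55 per arm reproduces.

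**2. Standard error.** SE = 27 × √(2/55) = 5.149 mm. Critical value t(0.95, 108) = 1.659.

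**3. How a baseline shift enters.** Let Δ be the true difference in pain reduction, 15 mg minus 60 mg. Let b be the amount by which elicitation raises the 15 mg baseline relative to the 60 mg baseline, with follow-up marks unaffected. The expected difference in change scores is then Δ + b. Non-inferiority is declared when the t statistic for (difference + 13) / SE exceeds 1.659. Its noncentrality is (13 + Δ + b) / 5.149.

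**4. Results.** The documents give no value for b, so the range is an assumption.

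| Size of b | Error rate at Δ = −13 when b favours 15 mg | Noncentrality | Power at Δ = 0 when b goes against 15 mg | Noncentrality |
|---|---|---|---|---|
| 0 mm | 0.050 | 0 | 0.806 | 13/5.149 = 2.525 |
| 2 mm | 0.104 | 2/5.149 = 0.388 | 0.684 | 11/5.149 = 2.136 |
| 3 mm | 0.143 | 3/5.149 = 0.583 | 0.612 | 10/5.149 = 1.942 |
| 5 mm | 0.248 | 5/5.149 = 0.971 | 0.460 | 8/5.149 = 1.554 |

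**5. Would baseline adjustment cure it?** No. In an ANCOVA with slope β on the same late baseline, the shift carries over as β × b. With an assumed β of 0.5 and b = 5 mm, 2.5 mm remains and the error rate is 0.123. This holds the SE at 5.149 for simplicity.

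**6. Is there an earlier baseline?** Section 12.5 requires at least 20 mm on the VAS, and section 10.1 requires inclusion criteria to be met before preparation, so some earlier reading is implied. None is described. The packet holds one pre-treatment form, two post-treatment forms and a spare for a form completed incorrectly, and VAS training is placed at drug preparation.

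**The case against.** The case on the other side has real force.

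- **The subject makes the mark.** Section 10.2 has the subject mark an unnumbered line after left-to-right instruction, with retraining only if the mark is invalid. Forms are not measured until all data collection is over. A reader might infer that the investigator coaches the score; the documents do not say so. These safeguards limit the risk. They do not remove it, because a dose-aware person still instructs and, if needed, retrains, and the form itself carries the dose.
- **The subject is not told the dose.** No disclosure to the subject is planned. It is possible only through the coded forms.
- **The timing conflict is slight.** A reader might infer from section 10.14 that the injection itself could affect the baseline rating. The VAS form description in section 10.1, the Medication Administration text and section 10.2 all make it pre-treatment. The wording in 10.14 is loose and needs alignment, no more.
- **The effect may partly cancel.** If the instruction changes how a subject uses the scale throughout, follow-up marks shift too. The figures above assume that only the baseline moves. Section 11.5 also attaches the SD of 27 to mean VAS, not explicitly to change.
- **The root is the dose-coded packet.** This stands, and it shapes the fix. The consent form is in the same packet, so re-ordering the steps alone would not conceal the dose.
- **An earlier baseline is an older one.** This also stands. Sections 13.1 and 13.4 allow a wait of minutes or hours before rooming, so a mark made straight after consent could be well out of date at injection.

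**Conclusion.** The point holds as a design weakness that is cheap to remove. The sequence is explicit: the dose is visible on the packet, told to the attending provider and prescribed, and only then is the one described pre-treatment VAS obtained, by an investigator who knows the arm. The primary analysis uses the unadjusted change from that mark.

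The documents show an unprotected step, not an actual bias. They give no basis for inferring that the baseline will be biased, or biased in favour of 15 mg. On the assumption of a 2 to 5 mm differential shift in the baseline alone, with SD 27 and 55 per arm, the error rate at the 13 mm margin would rise from 0.05 to 0.10–0.25 if the shift favours 15 mg. Power would fall from 0.81 to 0.68–0.46 if it goes the other way. The 30 and 60 minute assessments are also dose-aware. That is a separate blinding problem, which protecting the baseline does not solve.

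**What to change.** 1. In section 10.1, move VAS training and the pre-treatment mark to the point after consent, the review of systems and every eligibility check except attending concurrence with the randomised dose. That should be immediately before the allocation is opened and the attending provider is told the dose. Concurrence has to come later because it requires the dose to be known.
2. Use a pre-treatment form kept outside the dose-numbered packet, or give it a number without the dose, linked through the master key. The consent, HIPAA and eligibility forms are used earlier still, so they must not reveal the dose either.
3. Seal the completed form and name it as the baseline for the primary outcome. It can also serve the 20 mm criterion in section 12.5. In that case allow a check against 20 mm before sealing, since section 10.2 defers all measurement to the end of data collection.
4. Align the timing statement in section 10.14 with section 10.1 as revised.

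The cost is a wording change and new form numbering, with no change to 55 evaluable or 61 enrolled per arm. The baseline will be somewhat older at injection, by the time needed for attending concurrence, prescription and preparation. That delay should be similar in both arms.

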## **10.2 Data Collection:**

Describe all the data variables, information to be collected, the source of the data, and how the data will be operationally measured.

### **Primary Outcome Variable Data:**

The primary outcomes will be a clinically significant reduction in the numeric rating using the visual analog scale at 30 and 60 minutes from medication administration and compared to the pre-treatment VAS.

The primary outcome variables will be the change in subjective pain reported by patients using a VAS. The VAS is a validated measurement instrument used to record subjective reports of pain, or other subjective conditions. There are several different VAS constructs but this study will utilize a single horizontal line measuring 0-100 mm with short vertical marks as borders at each edge. All investigators will independently measure the VAS line to ensure that the printed line on the VAS form measures exactly 100 mm. The phrase "No pain" will be placed to the left of the 0 mm mark and the phrase "Severe Pain" will be placed to the right of the 100 mm mark. There will be no numerical or other incremental marks along, within or above the scale. The study subject will be instructed on the use of the scale prior to having their pain assessed. They will be informed that the scale measures from left to right, least to greatest level of pain. To annotate their pain level, they will be instructed to signify their level of pain on a scale of "0 mm or no pain at all" to "100 mm or Severe Pain" by making a single vertical mark through the horizontal VAS line on the document. If they do not make a vertical mark (circle, forward slash, backward slash, or otherwise), it is not through the horizontal VAS line, or illegible the investigator will retrain the patient on how to complete the form and a new form will be provided for the patient. An extra VAS is included in each Subject Study Packet for this purpose. Once completed, the forms will be returned to the subject study packet.

To measure the subject's reported level of pain on the VAS, the investigator will measure from the beginning of the scale to the vertical mark drawn by the subject. The "0 mark" on the metric tape measure will be aligned with the "0 mark" on the VAS form and the millimeters from the "0 mark" to the vertical line representing the subject's pain will be tallied. This distance will be annotated next to the scale for ease of reference. All VAS measurements will be completed and documented in the same manner for the 30 and 60 minute intervals. This study will use a previously validated measure of a 13 mm change in VAS to determine the minimum clinical significant difference (MCSD). (REF). Please refer to the statistical analysis portion of this document for more information about how this data will be used.

VAS measurements will not be taken during the data collection phase of this study. Only after data collection has been completed for the entire study and all VAS forms have been completed for all study subjects will the investigators actually measure and record the VAS scores. The purpose of not measuring the VAS at the time of data collection is to reduce research bias. Measurement of all VAS forms will take place at a predetermined time and place for both investigators (PI and AI). During the VAS measurement process, all investigators involved with the research must agree upon the measurement obtained. If, there is a discrepancy with the measurement process or measurement obtained, the VAS will not be used and the patient will be excluded from the study. The methodology for measuring the VAS will be based on prior literature explaining the process, in order to reduce inaccuracies 26.

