#### Randomization and Study Subject Packet Creation

Fully enrolled subjects will be randomized based on a two block randomization generated by the website [www.graphpad.com](http://www.graphpad.com). Randomization will be created so there are two groups (two block randomization), one which will receive 15 mg of intramuscular ketorolac and one which will receive 60 mg of intramuscular ketorolac. Each group (block) will consist of 61 subjects per the power analysis described later in this document and will be assigned a Subject Study Number.

The Subject Study Number will be comprised of a "K" for ketorolac, "15" or "60" designating which dose of ketorolac will be administered and then a specific number reflecting their position within the randomization block (randomization block number). For instance, a Subject Study Number of "K15-30" would signify that this patient was randomized into the ketorolac 15 mg group and the number 30 would reflect both the block to which the patient was randomized and confirm that the patient is indeed in the 15 mg group. Using both "15" or "60" and the randomization block number acts as a checks and balance to ensure that the patient is randomized into the correct group, and that the subject receives the correct randomized dose. Based on the randomization block number it is possible to know into which group the subject was randomized, the dose of ketorolac which will be administered and the order of the patient in the overall randomization. Following randomization, Subject Study Packets will be prepared.

Subject Study Packets will be prepared prior to the data collection (prior to the screening process). These packets will be created using manila envelopes capable of containing all study documents and which can be sealed. The contents of the envelopes will include the (1.) Ketorolac Research Form, (2.) Informed Consent Form (which includes consent for a POC UHCG), (3.) HIPAA Authorization Form, (4.) pretreatment VAS form, and two post-treatment VAS forms. None of the documents utilized or created throughout the study will be entered in to the subjects EHR. The manila packet and all documents contained within it will be annotated with the Subject Study Number (as described above). A description of these forms is listed below.

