3. HIPAA Authorization Form: signature of this document authorizes investigators use of the subject's protected health information (PHI) and personally identifiable information (PII) responsibly, securely and only for the purposes of this study. PHI and PII will be explained in detail to the patient and all questions will be honored. Should the patient decline to sign this document, they will be excluded from the study.
  1. PHI: The only protected health information used for this study will be the (1.) chief complaint and (2.) vital signs. A review of systems (ROS) will be used for inclusion and exclusion purposes of this study, but the EHR will not be accessed for this information and this information will not be documented on any media. A detailed description of the ROS is provided later in this application.
  2. PII: The only PII used for this study will be the (1.) subject name, (2.) age (in years-not date of birth), (3.) medical record number (MRN) and (4.) gender.

4. VAS forms (pretreatment and post-treatment): these are single page forms with a 0-100 mm VAS. Four separate VAS forms will be included in the Subject Study Packet and will be used to assess the subject's pain prior to administration of ketorolac, and at the 30 and 60 minute intervals after ketorolac administration. A fourth form will be included in the event that the patient completes the VAS incorrectly. The subject in each instance and on separate forms, will be asked to mark a horizontal line on the 0-100 mm continuum indicating their pre-treatment level of pain and their pain level post-treatment at the 30 minute and 60 minute intervals. Three separate forms are utilized to control for response bias. The Subject Study Number will also be included on the document, but otherwise no other information will be contained on the VAS forms.

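### A VAS reading the investigators cannot agree on removes the whole subject, with no tolerance or averaging, and the readers can see the dose on the form

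*Protocol*

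**What the plan says.** Under Primary Outcome Variable Data (Protocol section 10.2), the VAS forms are measured with a tape after all data collection has ended, in a session attended by both investigators. The stated reason for the delay is bias control: "The purpose of not measuring the VAS at the time of data collection is to reduce research bias". At that session "all investigators involved with the research must agree upon the measurement obtained". A discrepancy in either the measurement or the measuring process means that "the VAS will not be used and the patient will be excluded from the study".

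Three forms count for each subject: baseline, 30 minutes and 60 minutes (section 10.1, description of the VAS forms). The same item puts the Subject Study Number on each form. Under Randomization and Study Subject Packet Creation, that number contains 15 or 60, "designating which dose of ketorolac will be administered". Section 9.4 describes the trial as single-blinded.

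Section 11.5 raises the sample from 55 to 61 per arm for 10% dropout or withdrawal and does not mention exclusions at reading. The SAP says nothing about reader agreement, exclusions, analysis sets or missing VAS values.

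**The concern.** The penalty is out of proportion to the problem. A disagreement over one pen mark costs the subject's baseline, 30-minute and 60-minute scores. Taken literally, exclusion from the study also costs the adverse-event record, which is the secondary outcome. With three forms there are three chances of removal per subject.

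The decision is also made after randomisation, at the end of the study, by people who can read the dose on the form in front of them. Reading late keeps scores unknown during recruitment, but it does not hide the arm. Whether a discrepancy is resolved or left standing therefore decides who is analysed, and nothing masks that decision. In a non-inferiority trial, losing a few poor responders from the low-dose arm would favour the trial's hypothesis.

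**Working it through.** **Inputs from the plan (section 11.5).** Margin 13 mm, SD 27 mm, true difference 0, one-sided alpha 0.05, 55 evaluable per arm, 61 recruited per arm.

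**Reproducing the plan's figure.** For the equal-variance t-test, the noncentrality is 13 / (27 × √(2/n)). At n = 55 this is 13 / 5.149 = 2.52 on 108 degrees of freedom, and the exact power is 0.806. At n = 54 it is 0.7998. The stated 55 per arm for 80% power is confirmed. With all 61 per arm analysed, power is 0.841.

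**Loss from the rule.** Let q be the chance that a form ends with an unresolved discrepancy. The documents give no value, so q is an assumption, taken as independent across the three forms. The share of subjects excluded is 1 − (1 − q)³.

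| q per form | Subjects excluded | Left of 61 per arm | Power | Left of 55 per arm (planned dropout also occurs) | Power |
|---|---|---|---|---|---|
| 1% | 3.0% | 59.2 | 0.83 | 53.4 | 0.79 |
| 2% | 5.9% | 57.4 | 0.82 | 51.8 | 0.79 |
| 5% | 14.3% | 52.3 | 0.79 | 47.2 | 0.75 |

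Power is computed at the nearest whole number per arm.

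**When the allowance is used up.** Solve 61 × (1 − q)³ = 55: q = 1 − (55/61)^(1/3) = 0.034. A rate of about 3.4% per form consumes all 6 spare subjects per arm before any dropout.

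**What the exclusion buys.** Assume each reader has an error SD of 0.5 mm. The mean of two readings has error variance 0.25 / 2 = 0.125. A change score uses two forms, so it gains 2 × 0.125 = 0.25 mm² against 27² = 729, an increase of 0.03%. With an error SD of 1.0 mm and whole-millimetre recording, simulation gives an error variance of 0.541 for the averaged reading. The SD of the change is then √(729 + 2 × 0.541) = 27.02, and power at 55 per arm is 0.8057 instead of 0.8063. The required sample size does not change.

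**How much selective exclusion could matter (worst case, not an estimate).** This simulation sets the true difference at the 13 mm margin with 55 per arm. Removing the 1, 2 or 3 poorest responders from the 15 mg arm alone raises the one-sided type I error from 0.05 to about 0.08, 0.12 or 0.16.

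**The case against.** The best defence is that the text describes one joint session and one agreed measurement, which can fairly be read as consensus first, with exclusion only of what cannot be resolved. The protocol's usage supports this. Section 10.2 says so expressly when investigators are to measure independently (checking the length of the printed line), and its adverse-event text pairs agreement with conferring. Badly marked or illegible forms are also already replaced at the bedside after retraining. If two people confer over a ruler, unresolved discrepancies may be rare and the power cost small; the 1% and 2% rows above show that.

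This stands as far as the amount lost is concerned. A reader might infer that any 1 mm difference excludes a subject and that much of the sample would go. Independent whole-millimetre readings with an error SD of 0.1 to 0.3 mm would indeed mismatch on at least one form in 30% to 71% of subjects. The documents do not support that figure, because they do not describe independent readings compared afterwards and give no reader error.

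A reader might also infer that the randomised comparison is broken. That goes too far as well: difficulty in reading a pen mark has no stated link to arm, and the documents show an opportunity for biased exclusion, not its occurrence.

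The defence does not answer the rest. Neither discrepancy nor consensus is defined, an unresolved case still costs the whole subject, and conferring with the dose visible remains an unmasked decision. The dose-bearing code is a wider weakness that averaging alone does not cure.

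**Conclusion.** The point holds as a defect in the rule. As written, it allows a randomised subject to be dropped for a reader disagreement of any size, after unmasked reading, with no tolerance and no retention of that subject's other data. The loss cannot be known from the documents: about 3%, 6% or 14% of subjects at assumed unresolved rates of 1%, 2% or 5% per form, with about 3.4% enough to exhaust the dropout allowance. These figures rest on the assumed rates and on independence between a subject's forms. The benefit of the exclusion is nil at any plausible ruler error, which makes the rule hard to justify even if it is seldom used. The type I error figures show only what selective removal could do. The change should be made, but the rule does not by itself invalidate the design.

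**What to change.** Replace the exclusion sentence in section 10.2 with a rule along these lines. Each investigator records a separate reading of every form without seeing the other's value, and the mean of the two is used. Differences above a preset tolerance (for example 2 mm) are re-read and then averaged. No subject is excluded for reader disagreement or for a discrepancy in the measuring process. If a form truly cannot be read, only that time point is treated as missing, and the subject's other VAS scores and adverse-event data are kept. Repeat the rule in the SAP.

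Readings should go on separate sheets, because section 10.2 now has the distance written beside the scale, where a second reader would see it.

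Where feasible, cover the Subject Study Number or use a neutral form number during reading. Covering it leaves intact the dose check that section 10.1 builds into the code.

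The cost is a short text change, a second recording sheet, and masking or relabelling at most 122 × 3 = 366 forms. The readers and the scale stay the same. If forms have already been read under the present rule, re-read any that led to exclusion, restore those subjects, and report the number affected by arm.
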